Project Title: Optimizing Ankle Exoskeleton Assistance for Walking Across the Life Span

NCT Number: NCT04033146

Date: April 25, 2024

Study Protocol

We used commercially available bilateral ankle exoskeletons (Dephy Inc, Boxborough, MA) with custom controllers to provide plantarflexion assistance to each user. The exoskeletons have on-board encoders and inertial measurement units to enable state-based control.

Participants walked in six conditions: (1) without ankle exoskeletons (NoExo), (2) ankle exoskeletons without assistance (NoTorque, (3) exoskeletons with springlike assistance (Spring), and exoskeletons with three motorized assistance strategies with increasing peak torque: (4) 10 N-m (MotorLow), (5) 20 N-m (MotorMed), (6) 30 N-m (MotorHigh). The spring-like assistance used impedance control without damping to apply torque with a spring stiffness of 70 Nm/rad. The assistance began in the foot-flat position after heel strike and ended at toe off mimicking a spring and clutch mechanism than enabled storage and release of elastic energy in stance and free foot motion during swing. The torque profile for the motor assistance conditions was specified by a spline generated from four nodes: peak time, rise time, fall time, and peak torque. The spline settings were based on a previously published study that used human-in-the loop optimization to minimize metabolic cost for a group of younger adults walking at medium speed. For this experiment, we scaled the HiLO torque pattern to match our desired low, medium and high peaks values at preset values of 10, 20, and 30 N-m.

Participants completed testing over three sessions walking at 1.25 m/s on an instrumented split-belt treadmill (CAREN, Motek, Netherlands). The sessions were conducted in a set order: 1) habituation, 2) gait mechanics, and 3) steady-state metabolic energy consumption. Waiting periods between sessions were minimized to allow for learning and retention of walking patterns with exoskeleton assistance (2-7 days on average).

Session 1 – Habituation.

Previous work has shown the importance of habituation for the acceptance of assistance from exoskeletons. In the first session, each participant walked with spring-like assistance for three, seven-minute intervals for a total of 21 minutes. They also walked with motorized assistance for three, seven-minute intervals while increasing peak torque (10, 20, 30 Nm) with each bout.

Session 2 - Gait Mechanics.

The primary goal for the second session was to obtain biomechanical measurements. Reflective markers were placed on participants' lower limbs and torso to collect motion of the hip, knee and ankle joints and an instrumented treadmill was used to collect ground reaction forces form each limb. We instrumented participants with surface electromyography to record muscle activity on the right leg [tibialis anterior (TA), lateral gastrocnemius (LG), soleus (SOL), rectus femoris (RF), biceps femoris (BF), gluteus medius (GMd), and gluteus maximus (GMx)]. Participants were re-habituated to the exoskeleton assistance for 6-minutes prior to walking with exoskeletons without

assistance, with spring-like assistance, and with motorized assistance. During the motorized assistance habituation period, we increased the peak torque every 2 minutes. After each condition's habituation trial, participants walked for a 2-minute data acquisition period. The exoskeleton assistance order was randomized for each participant.

Session 3 - Steady-State Metabolic Energy Consumption.

Participants began the third session with a five-minute standing trial to record their metabolic resting baseline. Participants were fitted to a portable indirect calorimetry device (COSMED K5, Rome, Italy) to collect energy expenditure for each condition. We repeated the habituation process conducted during Session 2 - Gait Mechanics. The participants walked for six minutes in each of the six conditions in a randomized order with the respective habituation trial preceding a measurement trial.

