Project Title: Optimizing Ankle Exoskeleton Assistance for Walking Across the Life Span

NCT Number: NCT04033146

Date: April 25, 2024

Statistical Analysis Plan

The goal of the study is to evaluate the effects of bilateral ankle exoskeleton assistance on both young and older participants' metabolic energy cost during walking.

We seek to test three hypotheses:

H1. Bilateral ankle exoskeletons that provide 'motor-like' assistance will result in lower net metabolic power than those providing 'spring-like' assistance for young adults.

H2. Bilateral ankle exoskeletons that provide 'motor-like' assistance will result in lower net metabolic power than those providing 'spring-like' assistance for older adults.

H3. Bilateral ankle exoskeletons will result in lower net metabolic power for older versus young adults regardless of assistance strategy (i.e., for 'motor-like' or 'spring-like' assistance).

To test these hypotheses we will execute a repeated measures study design.

We will compute means of the primary outcome measure:

Net Metabolic Power (watts/kg)

for 6 bilateral ankle exoskeleton conditions:

- C1. Without ankle exoskeletons (NoExo) across
- C2. Bilateral ankle exoskeletons without assistance (NoTorque)
- C3. Bilateral ankle exoskeletons with spring-like assistance (Spring)
- C4. Bilateral exoskeletons with low-level motor-like assistance (10 Nm) (MotorLow)
- C5. Bilateral exoskeletons with medium-level motor-like assistance (20 Nm) (MotorMed)
- C6. Bilateral exoskeletons with high-level motor-like assistance (30 Nm) (MotorHigh)

for participants in two age categories:

X young adults (18-45 yrs)

Y older adults (>65 yrs).

To address H1 we will perform a two-way ANOVA on the young adult data (factors: participant (random) = X levels; exoskeleton condition = 6 levels) to test for a significant effect of exoskeleton condition on net metabolic power (watts/kg) ($p < \alpha = 0.05$; SPSS 21, IBM, USA). If exoskeleton condition is significant, we will perform post-hoc pairwise comparisons with a Bonferroni correction to test whether net metabolic power (watts/kg) is lower for MotorHigh vs. Spring; MotorMed vs. Spring; and MotorLow vs. Spring.

To address H2 we will repeat the analysis used for H1 on the older adult data.

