To address H3 we will compute mean differences with respect to NoTorque for spring-like (C4-C2) and motor-like (C6-C2; C5-C2; C4-C2) assistance conditions for both young and old adults. Then we will perform four independent t-tests with a Bonferroni

correction to test whether the difference in net metabolic power (watts/kg) is greater for older versus young adults for Spring, MotorLow, MotorMed, and MotorHigh bilateral exoskeleton assistance.

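### Device torque and stiffness are not scaled to body mass, so if the age groups differ in mass the planned H3 t-tests alone cannot separate age from assistance per kg

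*Protocol*

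**What the plan says.** The opening of the Study Protocol describes three motorised conditions, with the published torque pattern scaled to "match our desired low, medium and high peaks values at preset values of 10, 20, and 30 N-m". The spring-like condition is set to "apply torque with a spring stiffness of 70 Nm/rad". No scaling to body mass is described for either.

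The SAP names net metabolic power in watts/kg as the primary outcome and leaves the sizes of the two age groups as X and Y. H3 predicts lower net metabolic power "for older versus young adults regardless of assistance strategy". The analysis begins: "To address H3 we will compute mean differences with respect to NoTorque". It then applies four Bonferroni-corrected independent t-tests of older against young adults, one each for Spring, MotorLow, MotorMed and MotorHigh. I found no body mass summary, matching or covariate in either document.

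Two related details matter for the fix. The H3 paragraph labels the spring-like contrast C4-C2, which is the MotorLow contrast; the SAP's own list of conditions makes Spring C3. The Protocol is in the past tense ("Participants walked in six conditions"), so data may already have been seen.

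**The concern.** Dividing the outcome by body mass does not scale what the device delivers. A lighter person at a given setting receives more torque per kg. Subtracting NoTorque removes a person's baseline cost, but not a difference in response that comes from more or less assistance per kg.

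Age group cannot be randomised, so nothing in the design makes mean mass equal in the two groups. H3 is directional. If the older group is lighter, part of an apparent older-adult advantage could be extra assistance per kg. If it is heavier, part of a true advantage could be hidden. Without body mass by group, a reader of the H3 results cannot tell which case applies.

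H1 and H2 are not affected: they compare conditions within the same participants, who walked "in each of the six conditions in a randomized order".

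**Working it through.** The documents give no sample size, SD, effect size or body mass, so there is no planned figure to reproduce.

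**1. Assistance per kg (settings from the Protocol; masses illustrative).** Torque per kg = setting / mass.

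| Mass | 10 N-m | 20 N-m | 30 N-m |
|---|---|---|---|
| 60 kg | 0.17 | 0.33 | 0.50 |
| 90 kg | 0.11 | 0.22 | 0.33 |

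With group means of 65 and 75 kg, the lighter group gets 75/65 = 1.15 times the torque per kg at every setting. With 67.5 and 72.5 kg the ratio is 1.07.

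**2. Assumptions for size (none from the documents).** Response proportional to torque per kg, equal to -0.4 W/kg for 30 N-m at 70 kg; residual SD of the change 0.25 W/kg; mass SD 11 kg within each group; group means 70 kg plus or minus half the gap; mass floored at 45 kg; equal groups of 12 or 20. The SAP states alpha 0.05 for H1. I take it for H3 as well, two-sided, giving 0.05/4 = 0.0125 per test.

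**3. Spurious difference with no true age effect.** At 30 N-m and a 10 kg gap: 0.4 x 70 x (1/65 - 1/75) = 28 x 0.00205 = 0.057 W/kg. Allowing for the spread of mass within groups, simulation gives 0.060. At 20 and 10 N-m it gives 0.040 and 0.020.

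**4. Two-sided error per test, no true age effect (100,000 simulated trials per setting; repeat runs agree within 0.2 points).** Nominal 1.25%; cells are n=12 / n=20 per group.

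| Setting | 5 kg gap | 10 kg gap |
|---|---|---|
| 30 N-m | 1.6% / 1.8% | 2.5% / 3.6% |
| 20 N-m | 1.4% / 1.5% | 1.8% / 2.3% |
| 10 N-m | 1.2% / 1.2% | 1.4% / 1.5% |

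For Spring, 70 Nm/rad over an assumed 10 to 20 degrees is about 12 to 24 N-m. Error is then 1.3% to 1.6% at 5 kg and 1.5% to 2.6% at 10 kg.

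Varying the 30 N-m response from -0.2 to -0.6 W/kg and the residual SD from 0.15 to 0.40 gives 1.2% to 4.1% at 5 kg and 1.4% to 16% at 10 kg. The spurious difference at 10 kg is then 0.03 to 0.09 W/kg.

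**5. Masking.** Suppose a true older-adult advantage of 0.2 W/kg at 30 N-m and an older group 10 kg heavier. Power falls from 23% to 10% (n=12) and from 44% to 20% (n=20). With 1/mass in the model it is 19% and 38%.

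**6. Does the adjusted model behave?** I varied the response shape (no mass dependence, saturating, linear, 1/mass, 1/mass squared), torque, gap (5, 10, 15 kg), group size and covariate form (1/mass or mass): 180 settings. Adjusted error was 1.1% to 1.4% and adjusted bias at most 0.008 W/kg. Unequal groups, non-normal errors and other confounders were not tested.

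**7. Can the shift between the two estimates be read by eye?** No. With no mass dependence at all and a 10 kg gap, adjusted and unadjusted estimates still differ with SD 0.055 (n=12) or 0.039 W/kg (n=20). They differ by more than 0.05 W/kg in 29% or 18% of studies. When the assumed dependence is real, the shift has the wrong sign in 12% or 5% of studies at 30 N-m, and in 34% or 29% at 10 N-m.

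**8. Could chance alone produce a 10 kg gap?** With equal population means, the SD of the gap is 11 x sqrt(2/12) = 4.5 kg or 11 x sqrt(2/20) = 3.5 kg. A gap of 10 kg or more either way has probability 2.6% or 0.4%. Such a gap would mostly reflect who was recruited.

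**The case against.** The SAP defines the motor conditions by their absolute torque, so those H3 contrasts are already comparisons at fixed settings. Nothing shows the t-tests to be invalid for that question. This stands, and the t-tests should stay.

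A reader might infer that age and body mass cannot be separated in this study at all. The documents do not support that: an outcome in W/kg requires each participant's mass, so the data allow adjustment if the groups overlap in mass. The limit belongs to the planned tests alone.

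A reader might also infer that a mass gap exists, or that it favours one age group. The documents give no masses. Every error rate above rests on assumed inputs, and the base-case values are modest. If response does not depend on mass, there is nothing to correct.

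It is also fair to say that mass is only one of many ways in which observational age groups can differ. It deserves separate mention because the device settings link it directly to the amount of assistance, but adjusting for it cannot by itself establish an age effect.

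**Conclusion.** The point holds in a limited, conditional form and is an optional improvement. The H3 t-tests validly estimate the age-group difference at fixed device settings. If mass differs between groups and response depends on assistance per kg, they do not by themselves isolate age.

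Under the stated assumptions the effect is small at a 5 kg gap or at 10 N-m, and moderate at a 10 kg gap and 30 N-m. It is essentially zero when the two mass distributions match. Equal means alone are nearly enough: with 70 kg in both groups but SDs of 8 and 15 kg, the 1/mass model leaves about 0.01 W/kg.

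A tempting further reading is that an estimate moving towards or away from zero after adjustment shows mass dependence or masking. Step 7 shows that noise alone often produces such a shift, so it should not be read that way without an interval.

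**What to change.** Keep the four t-tests as planned and add the following to the SAP.

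- State that the unadjusted H3 tests address the age-group difference at fixed device settings.
- Report body mass (mean, SD) by age group.
- For each H3 contrast, fit one supporting linear model of change from NoTorque on age group plus 1/mass. Give its age-group estimate and 98.75% confidence interval (1 - 0.05/4) beside the t-test. Label it a sensitivity analysis if data have been examined.
- Report the 1/mass coefficient and the adjusted-minus-unadjusted shift, each with a confidence interval (a bootstrap would serve). Call H3 robust to body mass only as far as those intervals allow, and do not claim that mass adjustment alone establishes an age effect.
- Take Spring as C3-C2 in these models, and reconcile the C4-C2 label in the H3 paragraph with the SAP's list of conditions.

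The cost is a few sentences, one table row and one degree of freedom per model, with no new measurements. At a 10 kg gap and an assumed mass SD of 11 kg, the standard error rises by about 8% to 12%. At 30 N-m the 98.75% half-width goes from 0.28 to 0.31 W/kg (n=12) or from 0.21 to 0.23 (n=20). If masses balance, the standard error changes by -2% to +2%. No device setting changes.

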Project Title: Optimizing Ankle Exoskeleton Assistance for Walking Across the Life Span

NCT Number: NCT04033146

Date: April 25, 2024

Statistical Analysis Plan

The goal of the study is to evaluate the effects of bilateral ankle exoskeleton assistance on both young and older participants' metabolic energy cost during walking.

We seek to test three hypotheses:

H1. Bilateral ankle exoskeletons that provide 'motor-like' assistance will result in lower net metabolic power than those providing 'spring-like' assistance for young adults.

H2. Bilateral ankle exoskeletons that provide 'motor-like' assistance will result in lower net metabolic power than those providing 'spring-like' assistance for older adults.

H3. Bilateral ankle exoskeletons will result in lower net metabolic power for older versus young adults regardless of assistance strategy (i.e., for 'motor-like' or 'spring-like' assistance).

To test these hypotheses we will execute a repeated measures study design.

We will compute means of the primary outcome measure:

Net Metabolic Power (watts/kg)

for 6 bilateral ankle exoskeleton conditions:

- C1. Without ankle exoskeletons (NoExo) across
- C2. Bilateral ankle exoskeletons without assistance (NoTorque)
- C3. Bilateral ankle exoskeletons with spring-like assistance (Spring)
- C4. Bilateral exoskeletons with low-level motor-like assistance (10 Nm) (MotorLow)
- C5. Bilateral exoskeletons with medium-level motor-like assistance (20 Nm) (MotorMed)
- C6. Bilateral exoskeletons with high-level motor-like assistance (30 Nm) (MotorHigh)

for participants in two age categories:

X young adults (18-45 yrs)

Y older adults (>65 yrs).

To address H1 we will perform a two-way ANOVA on the young adult data (factors: participant (random) = X levels; exoskeleton condition = 6 levels) to test for a significant effect of exoskeleton condition on net metabolic power (watts/kg) ($p < \alpha = 0.05$; SPSS 21, IBM, USA). If exoskeleton condition is significant, we will perform post-hoc pairwise comparisons with a Bonferroni correction to test whether net metabolic power (watts/kg) is lower for MotorHigh vs. Spring; MotorMed vs. Spring; and MotorLow vs. Spring.

To address H2 we will repeat the analysis used for H1 on the older adult data.

To address H3 we will compute mean differences with respect to NoTorque for spring-like (C4-C2) and motor-like (C6-C2; C5-C2; C4-C2) assistance conditions for both young and old adults. Then we will perform four independent t-tests with a Bonferroni

correction to test whether the difference in net metabolic power (watts/kg) is greater for older versus young adults for Spring, MotorLow, MotorMed, and MotorHigh bilateral exoskeleton assistance.

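### H1 and H2: Holm over the three named Motor-vs-Spring contrasts would reject everything the gated Bonferroni plan rejects, and sometimes more; a cheap improvement, not an error

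*SAP*

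**What the plan says.** The SAP's paragraph on H1 begins with an omnibus test: "we will perform a two-way ANOVA on the young adult data", with factors "participant (random) = X levels; exoskeleton condition = 6 levels", at alpha 0.05. The contrasts come second and are conditional: "If exoskeleton condition is significant, we will perform post-hoc pairwise comparisons with a Bonferroni correction". Three are named in advance: "MotorHigh vs. Spring; MotorMed vs. Spring; and MotorLow vs. Spring". H2 follows the same route: "To address H2 we will repeat the analysis used for H1 on the older adult data".

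Three things are left open:
- **Divisor.** Bonferroni could divide by the 3 named contrasts or by all 15 pairs of six conditions.
- **Error term.** The contrasts could use the pooled ANOVA residual or the SD of each paired difference.
- **Sidedness.** The wording is directional ("to test whether net metabolic power (watts/kg) is lower for MotorHigh vs. Spring"), but no one- or two-sided level is given.

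The hypotheses say that motor-like "assistance will result in lower net metabolic power than those providing" spring-like assistance. They do not say that all three motor levels must beat Spring. The numbers of participants are the placeholders X and Y.

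**The concern.** The three contrasts are fixed in advance and carry their own multiplicity correction, so familywise control over them does not need the ANOVA. The ANOVA also includes NoExo and NoTorque, which appear in none of the three contrasts. Permission to test H1 therefore depends partly on conditions that H1 does not mention. Once the gate is passed, Bonferroni with divisor 3 holds every contrast to 0.0167, although a step-down rule with the same familywise guarantee would relax the later thresholds.

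At stake is which motor levels can be claimed to beat Spring in each age group. The gain falls mainly on the second and third contrasts, when more than one level works.

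**Working it through.** The plan states no power, sample size, SD or effect, so there is no figure of its own to reproduce. The check has an exact part and an illustrative part.

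**1. Containment (exact; only alpha = 0.05 and three contrasts are needed).**
- Bonferroni, divisor 3: reject if p < 0.05/3 = 0.0167. Familywise bound: 3 × 0.05/3 = 0.05.
- Holm: compare the ordered p-values with 0.05/3 = 0.0167, 0.05/2 = 0.025 and 0.05/1 = 0.05, stopping at the first failure. The familywise bound is also 0.05.
- If k p-values lie below 0.0167, the k smallest each pass their Holm step, because no Holm threshold is below 0.0167. So Holm rejects all that Bonferroni rejects.
- The gate can only remove rejections. Hence gated Bonferroni ⊆ Bonferroni ⊆ Holm.
- With divisor 15 the plan's threshold is 0.05/15 = 0.0033. Containment still holds, and the gap is wider.

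Holm can reject more in two ways. With the gate open and p = 0.010, 0.020, 0.040, Bonferroni (divisor 3) rejects one contrast and Holm three. With the gate closed and a contrast p below 0.0167, the plan rejects none and Holm at least one.

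**2. Size of the gain (illustrative).** Assumed: n=10 per age group, independent residuals with SD 0.15 W/kg in every condition, two-sided tests, divisor 3, paired error (df n−1 = 9), gate F-test on 5 and 5(n−1) = 45 df. Power was found by simulation, with at least 60,000 datasets per case. Effects are reductions relative to Spring.

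| Motor effects Low/Med/High (W/kg) | NoTorque vs Spring | All three: plan → Holm | At least one: plan → Holm |
|---|---|---|---|
| 0.15/0.15/0.15 | equal | 9% → 22% | 53% → 56% |
| 0.05/0.10/0.15 | equal | 1.2% → 4.0% | 31% → 37% |
| 0.15/0.15/0.15 | +0.15 | – | 56.4% → 56.4% |
| 0.05/0.10/0.15 | +0.15 | – | 37.5% → 37.6% |

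NoExo equals Spring throughout. With pooled error, the first row becomes 18% → 32% and 62% → 65%. At n=15 with paired error, all three rises from 26% to 46% (equal effects) or from 2.9% to 8.0% (graded).

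**3. Where the gain comes from.** In the first row, Holm with the gate kept gives 21.6% for all three, against 21.7% without it. That gain is almost entirely Holm's. With divisor 3, the gain in at least one rejection comes only from removing the gate. With divisor 15, the plan's first-row figure for at least one is about 26% instead of 53%, so the divisor matters there too.

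**4. Familywise error, n=10, no motor effect.**

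| SDs | Error term | All conditions equal: plan / ungated Holm | NoExo differs by 0.3: both |
|---|---|---|---|
| Equal (0.15) | paired | 1.5% / 4.5% | 4.6% |
| Equal (0.15) | pooled | 2.0% / 4.4% | 4.4% |
| 0.10 for NoExo and NoTorque, 0.20 for the rest | paired | Holm at most 4.7% | at most 4.7% |
| same unequal SDs | pooled | 4.3% / 9.2% | about 9.5% |

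In the last row a pooled residual understates the error of contrasts among the noisier conditions. The gate hides this when all six conditions are equal, but not when NoExo differs.

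**The case against.** **The plan is valid.** This stands. It names its contrasts and corrects for them, and with valid p-values familywise error is at most 5%. A reader might infer from the gate, or from the conservative Bonferroni step, that the SAP contains a statistical error. The documents do not support that.

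**The headline gain rests on a favourable pattern.** This also stands. The rise from 9% to 22% assumes three equal effects, whereas the motor levels are graded at 10, 20 and 30 Nm. With graded effects the rise is under 3 points. H1 and H2 do not require every level to win. For at least one rejection the gain is near zero if NoTorque costs more than Spring. The documents give no basis for choosing between these patterns. A reader might also take the gate to be costly in general, and that does not follow.

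**The p-values are not defined.** This limits the claim. Containment holds only with the same error term and sidedness in both procedures. If the plan meant pooled error and the revision moved to paired tests, the plan would reject something that Holm misses in 21% of datasets at n=10 with three equal effects.

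**Timing.** The Protocol reports conduct in the past tense ("Participants walked in six conditions") and bears the SAP's date, while the SAP is in the future tense. Whether data have been analysed cannot be told. If they have, moving to a less conservative test invites criticism.

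None of this reverses the direction: on identical p-values Holm cannot reject less.

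**Conclusion.** The point holds as an optional efficiency gain. The containment argument is certain. It needs no assumption about sample size, SD or effect, only that both procedures use the same p-values; the 5% bound further needs those p-values to be valid.

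The size is not certain. In the n=10, two-sided, paired, divisor-3 illustration, the gain in power for all three contrasts is about 3 to 13 points, depending on whether effects are graded or equal. For at least one it is about 3 to 6 points if NoExo and NoTorque equal Spring, and about zero if NoTorque costs 0.15 W/kg more. If the plan's divisor is 15, the gain is larger.

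Dropping the gate is straightforward with paired errors. With the pooled residual, the 5% level rests on equal variances of the paired differences (sphericity). All bounds are per age group; neither procedure controls error across H1, H2 and H3 together.

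**What to change.** In the H1 paragraph, and by reference for H2:

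1. Replace Bonferroni with Holm (0.0167, 0.025, 0.05) over exactly the three named contrasts, separately in each age group.
2. State that the family size is three, which error term is used, and whether the tests are one- or two-sided. This is worth doing even if Bonferroni is kept.
3. If contrast-specific paired errors are used, remove the condition that the ANOVA be significant and report the ANOVA descriptively.
4. If the ANOVA pooled residual is used, state the sphericity assumption. Removing the gate then carries the risk shown above (about 4.3% to 9.2% in the unequal-SD example). Holm with the gate kept still delivers most of the gain for all three contrasts.
5. If data have already been analysed, date and justify the change, and report the gated Bonferroni result beside the new one.

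The cost is a few sentences in the SAP and no new data. There are two downsides. Holm does not give the simple simultaneous confidence intervals that Bonferroni does. A change made after analysis loses part of its value, because both results must be shown and the choice of error term and sidedness is then itself open to question.

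### The H3 formula codes the spring-like difference as C4-C2, which is MotorLow; Spring is C3 and appears in no H3 contrast

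*SAP*

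**What the plan says.** The SAP's list of conditions gives NoTorque the code C2. The entry that matters most here is the one for the spring condition, "C3. Bilateral ankle exoskeletons with spring-like assistance (Spring". The lowest of the three motor settings has the code that follows it, C4, and is named MotorLow; MotorMed is C5 and MotorHigh is C6.

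The H3 paragraph then sets out the differences to be compared between age groups: "mean differences with respect to NoTorque for spring-like (C4-C2) and motor-like (C6-C2; C5-C2; C4-C2) assistance conditions". The sentence after that fixes the number of tests at four, with a multiplicity adjustment, and lists the conditions they cover; each age-group difference is to be tested for being "greater for older versus young adults for Spring, MotorLow, MotorMed, and MotorHigh bilateral exoskeleton assistance".

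**The concern.** The spring-like difference carries the code for MotorLow. C4-C2 therefore stands under two names in one formula, and C3 stands under none. The formula and the sentence that follows it specify different sets of tests.

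H3 is one of three hypotheses on net metabolic power, the primary outcome, and it is claimed for both assistance strategies. Spring-like assistance is one of those two strategies and is represented by a single condition, C3. An analysis programmed from the codes would run without any error message and would print a plausible row labelled Spring that contained no Spring data. A conclusion about spring-like assistance in older versus young adults would then rest on the 10 Nm motor condition.

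**Working it through.** **Step 1: match each named H3 test to its code.** The named tests come from the H3 paragraph, and the definitions come from the SAP's list of conditions.

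| Named test | Contrast as printed | What the printed contrast is | Contrast by the SAP's list |
|---|---|---|---|
| Spring | C4-C2 | MotorLow minus NoTorque | C3-C2 |
| MotorLow | C4-C2 | MotorLow minus NoTorque | C4-C2 |
| MotorMed | C5-C2 | MotorMed minus NoTorque | C5-C2 |
| MotorHigh | C6-C2 | MotorHigh minus NoTorque | C6-C2 |

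**Step 2: count.** The SAP states four tests. As printed, the contrasts are {C4-C2, C6-C2, C5-C2, C4-C2}, of which three are distinct; C3 is used 0 times. The stated four tests cannot be built from this set. With C3-C2 for Spring, the set is {C3-C2, C6-C2, C5-C2, C4-C2}: four distinct contrasts, one for each named condition. Only the spring-like entry is mismatched.

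**Step 3: rule out a different numbering.** The Protocol numbers its six walking conditions in the same order, with Spring third and MotorLow fourth. The motor-like list in the H3 paragraph also uses C4, C5 and C6 correctly. A second coding scheme does not explain the discrepancy.

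**Step 4: effect on multiplicity.** The SAP states alpha = 0.05 for the H1 ANOVA and does not restate it for H3. If 0.05 is taken as the H3 family level, Bonferroni over four tests gives 0.05/4 = 0.0125 per test. The divisor is four before and after the correction.

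**Step 5: illustration of the consequence if the code were followed literally.** The documents give group sizes only as X and Y and state no effect size or SD, so every input here is assumed: n = 10, 15 or 20 per group, a standardised age difference d in the MotorLow contrast, no age difference in the Spring contrast, and two-sided tests at 0.0125. The probability that the row labelled Spring is significant is then the power of a two-sample t-test, with 2n − 2 degrees of freedom and noncentrality d√(n/2). For example, n = 10 and d = 0.3 give 18 degrees of freedom, noncentrality 0.3 × √5 = 0.67 and critical value 2.775, hence 0.031.

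| d | n = 10 | n = 15 | n = 20 |
|---|---|---|---|
| 0.3 | 0.031 | 0.043 | 0.057 |
| 0.5 | 0.071 | 0.115 | 0.163 |
| 0.8 | 0.195 | 0.334 | 0.471 |
| 1.0 | 0.325 | 0.535 | 0.703 |

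The correct Spring contrast would be significant in 1.25% of trials under the same assumptions. If the directional wording of the H3 tests is read as one-sided at 0.0125, the range over this grid is 0.053 to 0.793.

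**The case against.** The best defence is that this is a slip that corrects itself. The word spring-like stands next to the wrong code, the reference condition is named, and the next sentence lists the four tests by condition. All of these point to C3-C2, and no other reading fits. The codes are used nowhere else in the analysis text, since the H1 and H2 comparisons go by condition name, and nothing says that the codes are programming variables. For harm to follow, an analyst would have to trust one code over the adjacent label and then overlook two identical result rows. On this view the matter is editorial, and the probabilities in the illustration are only t-test power over an assumed grid.

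Most of this stands. The intent can be recovered without asking the sponsor, literal execution is not shown, and the illustration does not measure how serious the error is. What does not stand is treating it as purely editorial. The mistake sits in the operative formula for a hypothesis on the primary outcome, and the formula and the list of tests give different answers to anyone reproducing the analysis. The divisor of four is consistent with the named tests; whether four is the right family across H1 to H3 is a separate question.

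**Conclusion.** The concern holds. As printed, the H3 formula gives three distinct contrasts for four named tests, duplicates MotorLow and omits Spring. That count rests only on the SAP's text and needs no assumption. H1 and H2 are unaffected. Any effect on results depends on the code having been followed literally, which the documents do not show. In that case, the false Spring row would be significant in about 3% to 70% of trials over the assumed grid, against 1.25% for the correct contrast, if MotorLow had an age effect and Spring had none. It should be fixed, but it does not call the design into question.

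**What to change.** In the SAP's H3 paragraph, change the spring-like entry from C4-C2 to C3-C2. Leave C4-C2, C5-C2 and C6-C2 for MotorLow, MotorMed and MotorHigh, and leave the Bonferroni correction at four tests.

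Then confirm that the analysis code reads C3 for the Spring row. A quick check is to compare the Spring and MotorLow rows of the H3 output: identical means, t and p in both would show that the printed code had been followed, and the Spring comparison would have to be rerun.

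The cost is one character in the SAP and a short code check. It needs no new data and no additional tests.
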